6.4.5. Vital signs/Physical examination

The absolute value and change versus baseline will be provided for vital signs (including BMI) by treatment group. Vital signs evaluation will include height [cm], weight [Kg], sitting blood pressure systolic/diastolic [mmHg], heart rate [beats/min] and temperature [°C] and body mass index (BMI). Body Mass Index (BMI) will be computed by dividing weight in kilograms by the square of height in meters. Body Mass Index [Kg/m2] will be also classified in the subsequent classes: "Underweight" if BMI lower than 18.5, "Normal" if BMI between 18.5 Kg/m2 and 24.9 Kg/m2, "Overweight" if BMI between 25 Kg/m2 and 29.9 Kg/m2 and "Obesity" if BMI greater than or equal to 30 Kg/m2.

Physical examination will be summarized as percentage of Normal and Abnormal body system evaluations at each time point by treatment group.

Physical Examination evaluation will include the result (reported as "Normal", "Abnormal" and "Not Done") of general appearance, eyes, ears, nose and throat, cardiovascular, respiratory, abdomen, urogenital, neurological, musculoskeletal, lymph nodes, dermatology and other system.

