## 5.2.3 Safety Endpoints

The safety endpoints of this study are as follows:

- Number of patients experiencing treatment-emergent adverse events (TEAEs) and serious adverse events (SAEs) from Baseline through end of study (EOS).
- Type, incidence, and severity of TEAEs and SAEs (Baseline through EOS).
- Changes from baseline to end of study of:
  - Vital signs and clinical laboratory tests (blood chemistry and hematology).
  - Physical examination.
  - Pulmonary function evaluated by Forced Vital Capacity (FVC), Forced Expiratory Volume at 1 second (FEV1), FVC/FEV1, Peak Expiratory Flow (PEF).
  - Cardiac function evaluated by ECG and ECHO.
  - Weight, height, and body mass index (BMI).

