# 12.2 Physical Examination

A complete physical examination (head, eyes, ears, nose, and throat, heart, lungs, abdomen, skin, lymph nodes, extremities and nervous system) will be performed at Screening (Visit 1) by a physician. In addition, medical history will be recorded at screening.

A limited physical examination to verify continued patient eligibility and to follow up on any change in medical history will be performed at the visits indicated in the Schedule of

17 June 2020 Page 73 of 110 Assessments, Table 5. All changes not present at baseline or described in the medical history and identified as clinically noteworthy must be recorded as AEs.

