To evaluate the impact of givinostat versus placebo administered chronically on quality of life and activities of daily living.	Quality of life test (SF-36): 1- Items 2- Domains: 1- Physical Functioning (PF) 2- Role-Physical (RP) 3- Bodily Pain (BP) 4- General Health (GH) 5- Vitality (VT) 6- Social Functioning (SF) 7- Role-Emotional (RE) 8- Mental Health (MH) 9- Total score	Mean changes in quality of life (SF-36) before and after 12 months of treatment with givinostat as compared to placebo.
	Adverse events	

ODUCCTIVES	VADIABLES	ENDROINTS
OBJECTIVES	VARIABLES	ENDPOINTS
To assess the safety and tolerability of givinostat versus placebo administered chronically.	Vital Signs: 1- Height 2- Weight 3- Body mass index (BMI) 4- Sitting blood pressure systolic 5- Sitting blood pressure diastolic 6- Heart rate 7- Temperature	Number and proportion of patients experiencing treatment-emergent adverse events (TEAEs) and serious adverse events (SAEs) from Baseline through end of study (EOS). Summary of type, incidence, and severity of TEAEs and SAEs (Baseline through EOS). Changes from baseline to end of study of vital signs.
	Laboratory tests: 1- Biochemistry 2- Hematology 3- Coagulation 4- Urinalysis	Changes from baseline to end of study of clinical laboratory tests.
	Physical examination	Changes from baseline to end of study of physical examination.
	Pulmonary function:	
	 Forced Vital Capacity (FVC) Forced Expiratory - Volume at 1 second (FEV1) FVC/FEV1 Peak Expiratory Flow (PEF) 	Changes from baseline to end of study of pulmonary function.
	Cardiac function parameters	

ODIFOTUES	MADIANIES	ENDROUNTS
OBJECTIVES	VARIABLES	ENDPOINTS
	1- ECG 2- ECHO	Changes from baseline to end of study of Cardiac function parameters.
To evaluate the pharmacokinetic (PK) profile of givinostat administered chronically in the target population	Details will be provided in a specific PK protocol.	Summary of the PK of givinostat and its major metabolites.
Secondary Exploratory objective(s):	Exploratory variable(s):	Exploratory endpoint(s):
To evaluate the correlation between the PK profile of givinostat and pharmacodynamics (PD) data.	Details will be provided in a specific Statistical Analysis Plan.	PK-PD correlation analyses between metrics of exposure and the efficacy/safety endpoints of givinostat.

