4.2. Definitions

Definition of Screening Failures

Screening failures are defined as patients who consent to participate in the clinical trial but are not subsequently randomly assigned to the study treatments.

Definition of Baseline

For all evaluations, the last available assessment collected during the screening phase or before the first study treatment dose, is considered as baseline assessment, with the exception of 6 Minute Walking Test whereby, if more than one value is recorded for the baseline, the mean value will be taken.

First/Last Administration of Study Treatment

The date of first administration of study treatment is the earliest start date when study treatment was administered and recorded on the "IMP Dosage" eCRF page.

Sponsor: ITALFARMACO
Protocol: DSC/15/2357/53

The date of last administration of study treatment is the last end date when study treatment was administered and recorded on the "IMP Dosage" eCRF page.

Study day

Study day is defined as the number of days from the study reference date to the visit/event date.

It is calculated as:

Study day = Visit/event date - Reference date + 1 day

If the visit/event date is before the reference date, then the study day is calculated as follows: Study day = Visit/event date - Reference date

The reference day is used to calculate the "Study day" variable it is defined as the date of the first drug administration. If this date is missing or not done, then the reference date will be null, and the study day will be not calculated.

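### The physical-examination endpoint is change from baseline, but the SAP plans only per-visit percentages of Normal and Abnormal findings, which cannot show within-patient change

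*SAP*

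**What the plan says.** The endpoint is worded as a change. Protocol 5.2.3 places physical examination under the line "Changes from baseline to end of study of", and the objectives table in SAP 2 repeats it as "Changes from baseline to end of study of physical examination".

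The only analysis is in SAP 6.4.5: "Physical examination will be summarized as percentage of Normal and Abnormal body system evaluations at each time point by treatment group". Each body system is recorded in one of three categories: Normal, Abnormal or Not Done. The section names no comparison with baseline and does not say whether Not Done counts in the denominator.

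The extent of the examination varies by visit. Protocol 12.2 describes a complete examination of listed systems ("lymph nodes, extremities and nervous system) will be performed at Screening (Visit 1"). For the other scheduled visits it says "A limited physical examination to verify continued patient eligibility and to follow up on any change in medical history will be performed", without listing the systems covered.

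On baseline, SAP 4.2 states that "the last available assessment collected during the screening phase or before the first study treatment dose, is considered as baseline assessment". Protocol 9.1.2 schedules a physical examination at Visit 3 and treats Visit 3 data as baseline for the study endpoints.

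**The concern.** An endpoint defined as change needs a summary that links each patient's end-of-study result to his baseline result. The planned table does not. A reader of the study report would see two prevalence figures per arm and could not tell a stable group from one in which some men developed findings while others lost them.

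There is a second, weaker worry. A percentage of evaluations depends on which evaluations were made. If the set of systems examined changes from visit to visit, the percentage can move although no patient has changed.

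At stake is the readability of one descriptive safety table. The primary analysis, the sample size and the alpha level are not affected.

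**Working it through.** The plan gives no figure for this endpoint, so there is nothing to reproduce. The check compares the sections and then uses simple arithmetic on labelled assumptions.

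**Step 1: endpoint against analysis, and how the SAP treats similar data**

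- Physical examination (SAP 6.4.5): percentages per visit only.
- Vital signs (SAP 6.4.5): value and change versus baseline.
- Pulmonary function, ECG and ECHO (SAP 6.4.6): value and change versus baseline.
- Laboratory data (SAP 6.4.4): change from baseline, plus shift tables to the worst on-treatment value.
- General rule for categorical data (SAP 4.1): frequencies or contingency tables, with no baseline-by-visit table named for physical examination.
- Protocol 13.8: summary descriptive statistics for physical examination, with no further detail.
- SAP 1.1 (changes from the protocol): nothing about dropping change for this endpoint.

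Physical examination is therefore the exception among these safety measures.

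**Step 2: what per-visit percentages can show**

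Take one body system and *n* patients examined at both visits. Let *a* be abnormal at both, *b* abnormal then normal (resolved), and *c* normal then abnormal (new).

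- Abnormal at baseline = (*a* + *b*)/*n*
- Abnormal at Visit 11 = (*a* + *c*)/*n*
- Difference = (*c* − *b*)/*n*

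Only *c* − *b* can be recovered, not *b* or *c*. For illustration take *n* = 34 (the planned givinostat arm) and assume 10 abnormal at each visit. Both percentages are 10/34 = 29.4% and the difference is 0. Then *b* = *c*, with any value from 0 to 10, so the number of patients whose status changed (*b* + *c*) lies anywhere from 0 to 20. This holds system by system and does not depend on how Not Done is handled.

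**Step 3: can the percentage move with no clinical change?**

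Assumptions that are not in the documents: results are pooled over systems; there are 11 systems (the SAP 6.4.5 list, taking eyes, ears, nose and throat as one and counting 'other'); the patient has one abnormal system throughout, and it is examined each time; *m* systems are examined at the visit.

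- Not Done excluded: abnormal = 1/*m*
- Not Done included: abnormal = 1/11, normal = (*m* − 1)/11

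| Systems examined (*m*) | Abnormal, Not Done excluded | Abnormal, Not Done included | Normal, Not Done included |
|---|---|---|---|
| 11 | 9.1% | 9.1% | 90.9% |
| 8 | 12.5% | 9.1% | 63.6% |
| 6 | 16.7% | 9.1% | 45.5% |
| 4 | 25.0% | 9.1% | 27.3% |
| 3 | 33.3% | 9.1% | 18.2% |

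If the abnormal system is not examined at the later visit, the abnormal figure becomes 0%. The direction and size of any movement therefore depend on choices that the SAP leaves open.

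**Step 4: which visits are being compared**

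The endpoint compares baseline with end of study. Under SAP 4.2 and Protocol 9.1.2, baseline is normally Visit 3. By Protocol 12.2 the examinations at Visits 3 and 11 are both limited. If the same systems are examined at both, *m* is the same and the percentage for an unchanged patient does not move. The contrast in the table is mainly Visit 1 against later visits. The examined set could still differ between Visits 3 and 11, because the limited examination follows up changes in medical history, but the documents do not show that it does.

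**The case against.** The strongest reply is that little is missing. Percentages at baseline and Visit 11 by arm do show the net change in prevalence, and Protocol 13.8 asked only for descriptive statistics, which the SAP supplies. Clinically noteworthy findings that are new since baseline must be recorded as adverse events under Protocol 12.2, so the safety signal that matters most has its own route into the report. All of this stands, and it keeps the point small. It does not answer Step 2: a net figure is not within-patient change, and the adverse-event route does not capture findings that resolve.

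A reader might also infer that the abnormal percentage must rise after screening simply because only the screening examination is complete. The documents do not support that. It requires pooling over systems with Not Done left out of the denominator, and SAP 6.4.5 states neither; a table for each system is an equally natural reading. It also requires that the abnormal systems are among those re-examined, and it contrasts Visit 1 with later visits, whereas the endpoint contrasts baseline, normally Visit 3, with Visit 11.

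Nor can one infer a bias between arms from the schedule alone, since both arms follow the same one.

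**Conclusion.** The mismatch between endpoint and analysis is established from the text. The endpoint is change from baseline to end of study, and the planned summary is a set of marginal percentages that cannot show within-patient change under any denominator. It would go too far to say that the endpoint is wholly unreported, because the net shift in prevalence by arm can be read from the table.

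The possible artefact from differing examinations is secondary. It can occur, because the limited examination is not itemised and the treatment of Not Done is not stated. Its size cannot be derived from the documents: the range in Step 3 rests on an assumed number of systems, an assumed single abnormality and an assumed pooling rule, and it concerns mainly Visit 1 against later visits.

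Overall this is a minor point, confined to one descriptive safety endpoint.

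**What to change.** In SAP 6.4.5 add, by arm and for each body system, a patient-level shift table from Normal or Abnormal at baseline to Normal or Abnormal at Visit 11. Restrict each table to patients with that system examined at both times, and show the number Not Done beside it.

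State that the SAP 4.2 baseline rule is applied system by system, so that the last pre-dose result is used; where a system was not examined at Visit 3, the Visit 1 result then serves. If the per-visit percentages are kept, state their denominator.

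The cost is SAP wording and one extra descriptive table. The data are already collected, and no visit or procedure changes. The gain is limited to this endpoint.

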6.4.6. Other safety parameters

The absolute value and change versus baseline will be provided for pulmonary function (including FVC, FEV1, FVC/FEV1, PEF) and cardiac parameters evaluated by ECG and ECHO.

Pulmonary Function Test will include forced expiratory volume in 1 second [L], forced vital capacity [L], peak expiratory flow [L/sec], fev1/fvc [%], percent predicted fev1 [%], percent predicted fvc [%], forced expiratory flow 25-75% [L/sec], percent predicted fev1/fvc [%] and percent predicted fef25-75 [%].

12-leads ECG evaluation will include RR Interval Aggregate [msec], ECG Mean Ventricular Rate [beats/min], PR Interval Single Beat [msec], QRS Duration Single Beat [msec], QT Interval Single Beat [msec], QTcF Interval Single Beat [msec] and Interpretation.

The incidence of outliers in QTcF intervals (>450, >480, and >500 msec), and the change from baseline in QTcF intervals (>30 and >60 msec) will be summarized by visit and overall for each treatment group as defined in ICH E14 guideline (ICH_E14, 2005). Where triplicate ECG assessments have been performed, the mean of the non-missing values will be used to

Sponsor: ITALFARMACO Protocol: DSC/15/2357/53

determine outliers. A subject will be counted once for each outlier in the overall summary if they experienced at least one occurrence of that outlier

Echocardiography evaluation will include mitrial insufficiency, severity (indicated as "Mild", "Moderate" or "Severe"), left ventricular end-diastolic internal dimension (LVEDD) [mm], left ventricular end-systolic internal dimension (LVESD) [mm], left ventricular septal wall thickness (LVS) [mm], left ventricular posterior wall thickness (PW) [mm], left ventricular end-diastolic (LVED) volume (4-ch) [ml], left ventricular end-diastolic (LVED) volume (Biplane) [ml], left ventricular end-systolic (LVES) volume (4-ch) [ml], left ventricular end-systolic (LVES) volume (2-ch) [ml], left ventricular end-systolic (LVES) volume (Biplane) [ml], left ventricular outflow tract (LVOT) diameter [mm], left ventricular ejection fraction (LVEF) [%], method of left ventricular ejection fraction calculation (LVEF) (indicated as "2-ch", "4-ch" or "Biplane"), mitral E max velocity [cm/s], mitral A max velocity [cm/s], LVOT TVI [cm], tricuspid regurgitation v max [ms], isovolumic relaxation time (Left Ventricle) [m/s] and mitral E' (lateral) [cm/s].

6.5. Subgroup Analyses

The subgroups are defined as below:

Subgroup	Definition		
LTBP4	IAMM, VTTT+Other		
SPP1	TT, GG+GT		
Mutated exon(s) data	Exon 45, Prior to exon 45, Post-exon 45		

The following analyses will be repeated for each subgroup defined above:

- Change from baseline to 12 months of treatment with givinostat or placebo in total fibrosis (%)
- Change from baseline to 12 months of treatment with givinostat or placebo in MRS
 Fat Fraction in the vastus lateralis muscles
- Change from baseline to 12 months of treatment with givinostat or placebo in MRS
 Fat Fraction in the soleus muscles
- Change from baseline to 12 months of treatment with givinostat or placebo in MFM total score
- Change from baseline to 12 months of treatment with givinostat or placebo in 6MWT (Distance walked after 6 minutes)
- Change from baseline to 12 months of treatment with givinostat or placebo in functional test velocity (i.e. 4-Stair ascent duration, Rising from floor duration, 10-Metre Walk/Run test duration)

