## 5.2.5 Exploratory Endpoints

The exploratory endpoints of this study are the following:

- PK-PD analyses of the relationship between metrics of exposure and the efficacy/safety endpoints of givinostat.
- Analyses to explore whether the effects of givinostat versus placebo administered chronically may be related to the type of LTBP4 or Osteopontin genotype.
- Evaluation of serum circulating proteins, by an ELISA based system, as potential biomarkers for BMD.
- Additional evaluations of other muscle image parameters assessed by MRI (details will be provided in a specific imaging protocol).

17 June 2020 Page 42 of 110

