3.5. Sample Size and Power Estimation

The hypothesis to be tested in this study is as follows:

$$H_0: \mu_G - \mu_P = 0$$
 vs $H_1: \mu_G - \mu_P \neq 0$

where μ_G and μ_P the mean change from baseline to 12 months in total fibrosis (%) for the givinostat and placebo groups respectively.

The primary hypothesis to be tested in this study is that total fibrosis (%) will increase less in the givinostat group than in the placebo group so the primary efficacy variable of the study is the mean change from baseline to 12 months in total fibrosis (%).

Ver.04 25Jun2020

Sponsor: ITALFARMACO Protocol: DSC/15/2357/53

A sample size of 48 patients with evaluable baseline biopsies (in a 2:1 ratio, 32 and 16 respectively) will provide 80% power to test the null hypothesis of no treatment effect (givinostat – placebo) on total fibrosis vs the alternative hypothesis that the treatment effect is \geq 9% using a two-sided t-test with alpha level of 5% and assuming a common SD of 10% (with the SD being based upon blinded interim data from first 20 patients with valid biopsies).

Allowing for an approximate 5% of patients with not evaluable biopsies, the total number of patients to be randomized is 51 (i.e. 34 in givinostat arm and 17 in placebo arm).

After the first 20 baseline muscle biopsies was collected, an interim blinded sample size reassessment was undertaken to check the SD assumption used in sizing the trial. Details are capture in the specific SAP for the Interim Analysis.

After study enrollment was completed and baseline data were collected for all patients, a second blinded interim analysis was performed to obtain a preliminary overview of the baseline patient characteristics.

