A Mixed Model will be fitted to the data with the difference between log visit 11 and log baseline values as the dependent variable; log baseline as a covariate, treatment will be included as independent class variables and treatment by sequence interaction. The sequence of biopsy site (Right-Left, Left-Right) will be included as a fixed effect and subject as a random effect to evaluate the difference in Total Fibrosis between biopsy sites.

If the treatment by sequence interaction is p>0.10, then the model without the interaction term will be presented.

Data handling rules

Primary analysis will be based on observed data only.

Sensitivity analysis for the primary endpoint will be performed as follow:

- 1. Multiple imputation for missing data:
 - a. Missing baseline primary endpoint data will be imputed as the geometric mean of all non-missing baseline primary endpoint values across the randomized treatment groups. Visit 11 missing data will be imputed (on the log scale) under a Missing At Random (MAR) assumption using SAS procedure MI within each treatment group using distribution implied by the non-missing patient data for that treatment group. A total of 20 imputation runs will be performed. Post imputation, each imputed dataset will be analysed separately exactly as described for primary efficacy analysis. The SAS procedure MIANALYZE will then be used to combine the 20 datasets of estimates by Rubin's rules. The resulting multiply imputed means and difference in means will be presented, along with the associated SEs, 2-sided 95% CIs and 2-sided p-values.
 - b. Missing baseline primary endpoint data will be imputed as the geometric mean of all non-missing baseline primary endpoint values across the randomized treatment groups. Visit 11 missing data will be imputed (on the log scale) under a Missing Not At Random (MNAR) assumption using SAS procedure MI for both randomized treatment groups using the distribution implied by the non-missing patient data within the placebo group. A total of 20 imputation runs will be performed. Post imputation, each imputed dataset will be analysed separately exactly as described for primary efficacy analysis. The SAS procedure MIANALYZE will then be used to combine the 20 sets of estimates by Rubin's rules. The

Sponsor: ITALFARMACO
Protocol: DSC/15/2357/53

resulting multiply imputed means and difference in means will be presented, along with the associated SEs, 2-sided 95% CIs and 2-sided p-values.

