The absolute values of distance walked after 1, 2, 3, 4, 5, 6 minutes, number of falls and their changes versus baseline will be summarized as continues variables too. In addition, a box-plot of the mean 6MWT at each time-point will be produced for each visit by treatment group.

To make best use of repeated intra-subject evaluations of 6MWT, the absolute change from baseline to visits 8, 9 10 and 11 (months 3, 6, 9 and 12) will computed. These data will be analyzed using mixed model repeated measures (MMRM) analysis. Fixed effect class terms will be included for treatment, visit, visit x treatment interaction and concomitant steroid use at baseline; baseline value will be included as a covariate. An unstructured covariance matrix will be used to model the within-subject error. LSmeans and SEs and also the difference in LSmeans between treatments will be extracted by visit; SEs, 2-sided 95% CIs and 2-sided p-values will also be extracted for the difference in LSmeans. The principal focus of inference will be the results at visit 11 (month 12). Possible need for log transformation of this variable will be assessed by check of ANCOVA model residuals. If considered non-Normal, a supportive analysis will be performed on the log scale.

Worsening is defined as a reduction in the distance walked after 6 minutes, as assessed by 6MWT, after 12 months of therapy compared to baseline.

Sponsor: ITALFARMACO
Protocol: DSC/15/2357/53

The proportion of patients with <10% worsening, at each time point after baseline, will be summarized as a discrete variable using descriptive statistics.

The proportion of patients with <10% worsening in 6MWT after 12 months of therapy will be compared between arms using a stratified Cochran Mantel-Haenszel (CMH) chi square test with a two-sided α =0.05 level. The stratification factor is concomitant steroid use at baseline. The proportion, along with its exact two-sided 95% CI, will be computed within each treatment group. A two-sided 95% CI for difference of proportion between the treatment groups will also be computed. Patients where there are missing data such that <10% worsening in 6MWT after 12 months cannot be determined will be included in the analysis as having worsened.

The proportion of patients who lose ambulation during the study (6MWT not done because patient unable to physically perform the test), at each time point after baseline, will be summarized as a discrete variable using descriptive statistics.

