6.3.3. Exploratory efficacy analysis

Evaluation of LTBP4 and osteopontin genotype

In order to determine whether the effects of givinostat versus placebo are related to the type of Mutation Exon or the LTBP4 and Osteopontin (i.e. SPP1) genotypes, three further subgroups of subjects will be defined: Mutation Exon (Exon 45, Prior to exon 45, Post-exon 45), LTBP4 (IAMM, VTTT, Other, VTTT+Other) and SPP1 (TT, GT, GG, GG+GT).

The number and proportion of patients in each subgroup will be summarized as appropriate. Further analyses are described in Section 6.5.

Evaluation of the functional test velocity

Velocity for each functional test will be computed at each visit from the following variables:

- 4-Stair ascent duration
- Rising from floor duration
- 10-Metre Walk/Run test duration

For patients with missing data TFT data due to lack of ability to perform the test, their velocity will be set equal to zero.

Velocity to 4-Stair Climb will be calculated according to the following formulas:

$$Velocity_{4-Stair\ Climb} = \frac{4}{time\ to\ climb\ 4\ stair}$$

Sponsor: ITALFARMACO
Protocol: DSC/15/2357/53

The velocity will be set to zero for patients who don't attempt the test with reason "Unable to physically perform the test" or for patients with the lowest grade (1) for the 4 Stair Climb test.

The absolute value of velocity to 4-Stair Climb and change versus baseline, at each time point, will be summarized as continuous variables using descriptive statistics.

To make best use of repeated intra-subject evaluations of 4-Stair Climb velocity, the absolute change from baseline to visits 8, 9 10 and 11 (months 3, 6, 9 and 12) will be analyzed using mixed model repeated measures (MMRM) analysis. Fixed effect class terms will be included for treatment, visit, visit x treatment interaction and concomitant steroid use at baseline; baseline value will be included as a covariate. An unstructured covariance matrix will be used to model the within-subject error. LSmeans and SEs and also the difference in LSmeans between treatments will be extracted by visit; SEs, 2-sided 95% CIs and 2-sided p-values will also be extracted for the difference in LSmeans. The principal focus of inference will be the results at visit 11 (month 12).

Velocity to walk/run 10 m will be calculated according to the following formula:

$$Velocity_{walk/run \ 10 \ m} = \frac{10}{time \ to \ walk/run \ 10 \ m}$$

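### SAP 6.5 repeats the analyses within each genotype and exon subgroup but plans no estimate of how the treatment effect differs between subgroups, which is the question SAP 6.3.3 sets

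*SAP*

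**What the plan says.** Protocol 5.2.5 lists as an exploratory endpoint: "Analyses to explore whether the effects of givinostat versus placebo administered chronically may be related to the type of LTBP4 or Osteopontin genotype". Protocol 13.9 leaves the details to the SAP. SAP 6.3.3 widens the aim to include exon: "In order to determine whether the effects of givinostat versus placebo are related to the type of Mutation Exon or the LTBP4 and Osteopontin" genotypes. It plans counts and proportions per subgroup, then adds: "Further analyses are described in Section 6.5".

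SAP 6.5 defines two two-level factors (LTBP4, SPP1) and one three-level factor (mutated exon) and states: "The following analyses will be repeated for each subgroup defined above". The list covers total fibrosis, MRS fat fraction in two muscles, MFM total score, 6MWT distance and the functional-test velocities (three tests). It names no subgroup term, no treatment-by-subgroup term, no comparison between subgroup effects and no rule for reading differences across subgroups.

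The SAP does specify interactions elsewhere. One is treatment by biopsy sequence (6.3.1 and 6.3.2.3): "If the treatment by sequence interaction is p>0.10, then the model without the interaction term will be presented". The other is visit by treatment in the repeated-measures models: "Fixed effect class terms will be included for treatment, visit, visit x treatment interaction and concomitant steroid use at baseline". PK-PD, serum and MRI biomarkers are sent to separate plans; genotype and exon are not.

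**The concern.** Whether an effect depends on genotype is a question about the difference between two treatment effects. An analysis repeated in each subgroup gives each effect separately and leaves the difference to be judged by eye. The easy reading is to see a significant result in one stratum, none in the other, and conclude that the drug works in only one genotype. With strata this small, that pattern is common even when the effect is the same everywhere. At stake is a misleading hypothesis about which patients respond, carried into later trials. The primary comparison is not at stake.

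**Working it through.** **Inputs (SAP 3.5).** Difference 9 points, SD 10, two-sided alpha 0.05, 32 givinostat and 16 placebo.

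**The plan's own figure.** SE = 10 × √(1/32 + 1/16) = 3.06, so the noncentrality is 9/3.06 = 2.94 on 46 df. Noncentral-t power is 82.1%; with 30 + 15 it is 79.4%. So 48 is the smallest 2:1 total that reaches 80%. For 5% unevaluable biopsies, 48/0.95 = 50.5, rounded up to 51. Both stated sizes reproduce.

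**Assumptions added.** The documents give no subgroup prevalences, so splits of 50/50, 70/30 and 80/20 are assumed, with 2:1 allocation kept inside each subgroup. The last two imply fractional patients. The test is an unadjusted t-test on the percentage-point scale, because the sample-size inputs are on that scale.

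**Step 1: same true effect of 9 points in both subgroups.** With within-subgroup powers p and q, the chance that exactly one is significant is p(1 − q) + q(1 − p).

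| Split | Larger subgroup | Smaller subgroup | p | q | Exactly one significant |
|---|---|---|---|---|---|
| 50/50 | 16 + 8 | 16 + 8 | 51.1% | 51.1% | 50.0% |
| 70/30 | 22.4 + 11.2 | 9.6 + 4.8 | 66.4% | 31.8% | 56.0% |
| 80/20 | 25.6 + 12.8 | 6.4 + 3.2 | 72.5% | 21.1% | 63.0% |

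Rounding to whole patients changes little: 22 + 11 against 10 + 5 gives 55%, and 24 + 12 against 8 + 4 gives 59%.

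For three equal exon groups, power is 35.3% in each. The chance of a mixed pattern is 1 − 0.353³ − 0.647³, about 68%.

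**Step 2: smaller common effect, 50/50 split.** The chance is 2p(1 − p).
- 6 points: p = 26.3%, giving 39%.
- 4.5 points: p = 16.9%, giving 28%.
- No effect: p = 5%, giving 9.5%.

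**Step 3: what a direct interaction estimate would deliver.** SE of the difference in effects = 10 × √(1/nG1 + 1/nP1 + 1/nG2 + 1/nP2), on 48 − 4 = 44 df, t = 2.015.

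| Split | SE | 95% CI half-width | Power for a 9-point interaction |
|---|---|---|---|
| 50/50 | 6.12 | 12.3 | 30% |
| 70/30 | 6.68 | 13.5 | 26% |
| 80/20 | 7.65 | 15.4 | 21% |

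For exon, with a 9-point effect in one of three equal groups and none in the others, a 2-df test has about 21% power.

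**The case against.** Two stronger readings are tempting, and the documents support neither.

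A reader might infer that the plan makes the question unanswerable. It does not. The strata of each factor are disjoint, so if the subgroup estimates and standard errors are reported, the contrast and its interval can be formed by hand. The gap is that the SAP does not plan this.

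A reader might also infer that the trial would probably report a genotype-dependent effect that does not exist. SAP 6.3.3 and 6.5 do not say that subgroups will be compared by which of them reach significance, and the repeated primary analysis yields differences with confidence intervals. The 50 to 68% is the chance of a discordant pattern, not of a reported claim.

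Further limits stand. The splits are assumed, the true effect may be below 9 points, and the planned main fibrosis analysis is a log-scale ANCOVA. The figures concern fibrosis, one of eight endpoints. Exon is an aim only in SAP 6.3.3; the protocol endpoint names LTBP4 and osteopontin. The work is exploratory, and a direct interaction estimate would be imprecise.

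None of this supplies the missing contrast. Exploratory status does not turn within-subgroup results into a between-subgroup comparison. The imprecision favours reporting the interval, which shows how little 48 patients can say, whereas separate subgroup results tend to hide it.

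**Conclusion.** The point holds as a gap between a stated question and its planned analysis. SAP 6.3.3 asks about effect modification, and SAP 6.5 plans no estimate or interval for it. If the effect is truly 9 points everywhere, a discordant pattern across two subgroups arises in about 50 to 63% of trials, and a mixed one across three equal exon groups in about 68%. At a 50/50 split the two-subgroup figure drops to 39%, 28% and 9.5% as the common effect falls to 6, 4.5 and 0 points. All of these rest on assumed prevalences and a raw-scale t-test. This is a low-cost improvement to an exploratory analysis.

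**What to change.** In SAP 6.5, for each factor and each listed endpoint, fit one model on all ITT patients.

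- **ANCOVA endpoints** (total fibrosis on the log scale, the two MRS fat fractions): add subgroup and treatment-by-subgroup to the planned model.
- **Repeated-measures endpoints** (MFM total score, 6MWT, three velocities): add subgroup, subgroup-by-visit, treatment-by-subgroup and treatment-by-subgroup-by-visit, and take the contrast at visit 11 (month 12). A treatment-by-subgroup term alone would force the same effect modification at every visit and would not give the month-12 contrast.
- **Reporting:** give the interaction estimate with its 95% CI (for log-scale fibrosis, a ratio of treatment ratios) and the subgroup-specific effects from the same model. Label all subgroup p-values exploratory and descriptive. State that a non-significant interaction is not evidence of a uniform effect.

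The cost is a short SAP revision and a few model terms per endpoint, with no new data. The downside is a wide interval.
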